#### 5.1.3 Subject Exclusion Criteria

The subject must be excluded from participating in the trial if the subject:

- 1. Is currently participating in and receiving study therapy or has participated in a study of an investigational agent and received study therapy or used an investigational device within 4 weeks of the first dose of treatment.
- 2. Has a diagnosis of immunodeficiency or is receiving systemic steroid therapy at doses ≥ 10 mg prednisone or any other form of systemic immunosuppressive therapy within 7 days prior to the first dose of trial treatment. Subjects are permitted to use topical, ocular, intra-articular, intranasal, and inhalational corticosteroids (with minimal systemic absorption). Physiologic replacement doses of systemic corticosteroids are permitted, even if > 10 mg/day prednisone equivalents. A brief course (≤28 days) of corticosteroids for prophylaxis (eg, contrast dye allergy) or for treatment of non-autoimmune conditions (eg, delayed-type hypersensitivity reaction caused by contact allergen) is permitted.

- 3. Has a known history of TB Disease (Mycobacterium tuberculosis)
- 4. Hypersensitivity to pembrolizumab, vorinostat or any of its excipients
- 5. Patients enrolled on the phase II randomized trial, who have had prior treatment with a PD1 or PDL1 inhibitor, anti-CTLA 4 antibody or any other antibody or drug that specifically targets immune checkpoint pathway (i.e. not "immune therapy naïve").
  - -Note: For those enrolled in the phase I dose escalation, prior use of a PD1 or PDL1, anti-CTLA4 antibody or any other antibody or drug that specifically targets immune checkpoint pathway is allowed. For those enrolled in the phase IB, prior use of a PD1 or PDL1, anti-CTLA4 antibody or any other antibody or drug that specifically targets immune checkpoint pathway is required. For all patients in all phases, prior use of a vaccine for treatment of cancer is allowed.
- 6. Patients enrolled in the phase Ib expansion who have never previously been treated with a PD1 or PDL1 inhibitor, anti-CTLA 4 antibody or any other antibody or drug that specifically targets immune checkpoint pathway in the past (i.e. not "pre-treated")
- 7. Patients who have received thoracic radiation >30Gy within six months of the first dose of pembrolizumab.
- 8. Patients taking any HDACi other than vorinostat.
- 9. Has had a prior anti-cancer monoclonal antibody (mAb) within 4 weeks prior to study Day 1 or who has not recovered (i.e., ≤ Grade 1 or at baseline) from adverse events due to agents administered more than 4 weeks earlier.
- 10. Has had prior chemotherapy within 3 weeks, or targeted small molecule therapy or radiation therapy within 2 weeks prior to study Day 1 or who has not recovered (i.e., ≤ Grade 1 or at baseline) from adverse events due to a previously administered agent.
  - -Note: Subjects with ≤ Grade 2 neuropathy are an exception to this criterion and may qualify for the study.
  - -Note: Subjects with any grade alopecia are an exception to this criterion and may qualify for the study.
- 11. If subject received major surgery, they must have recovered adequately from the toxicity and/or complications from the intervention prior to starting therapy.
- 12. Has a known additional malignancy that is progressing or requires active treatment. Exceptions include basal cell carcinoma of the skin or squamous cell carcinoma of the skin that has undergone potentially curative therapy, or in situ cervical cancer.
- 13. Has known active central nervous system (CNS) metastases and/or carcinomatous meningitis. Subjects with previously treated brain metastases may participate provided they are stable (without evidence of progression by imaging for at least four weeks prior to the first dose of trial treatment and any neurologic symptoms have

returned to baseline), have no evidence of new or enlarging brain metastases, and are not using steroids in doses greater than 10 mg of prednisone daily (or equivalent) for at least 7 days prior to trial treatment. This exception does not include carcinomatous meningitis which is excluded regardless of clinical stability.

- 14. Has active autoimmune disease that has required systemic treatment in the past 2 years (i.e. with use of disease modifying agents, corticosteroids in doses greater than 10 mg of prednisone daily (or equivalent) or immunosuppressive drugs). Replacement therapy (eg., thyroxine, insulin, or physiologic corticosteroid replacement therapy for adrenal or pituitary insufficiency, etc.) is not considered a form of systemic treatment. Subjects are permitted to enroll if they have vitiligo, type I diabetes mellitus, residual hypothyroidism due to autoimmune condition only requiring hormone replacement, psoriasis not requiring systemic treatment, or conditions not expected to recur in the absence of an external trigger.
- 15. Has an active infection requiring systemic therapy.
- 16. Has a history or current evidence of any condition, therapy, or laboratory abnormality that might confound the results of the trial, that would substantially increase risk of incurring adverse events (AEs) from the study medications, that would interfere with the subject's participation for the full duration of the trial, or is not in the best interest of the subject to participate, in the opinion of the treating investigator.
- 17. Has known psychiatric or substance abuse disorders that would interfere with cooperation with the requirements of the trial.
- 18. Is pregnant or breastfeeding, or expecting to conceive or father children within the projected duration of the trial, starting with the pre-screening or screening visit through 120 days after the last dose of trial treatment.
- 19. Has a known history of Human Immunodeficiency Virus (HIV) (HIV 1/2 antibodies).
- 20. Has known active Hepatitis B (e.g., HBsAg reactive) or Hepatitis C (e.g., HCV RNA [qualitative] is detected).
- 21. Has received a live vaccine within 30 days of planned start of study therapy.

Note: Seasonal influenza vaccines for injection are generally inactivated flu vaccines and are allowed; however intranasal influenza vaccines (e.g., Flu-Mist®) are live attenuated vaccines, and are not allowed.

- 22. Has a history of, or any evidence of activenon-infectious pneumonitis that required or requires steroids.
- 23. Has evidence of interstitial lung disease
- 24. Has a history of symptomatic (NYHA class II-IV) heart failure.

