#### 2.0 TRIAL DESIGN

#### 2.1 Trial Design

We propose a phase I/randomized phase II clinical trial of pembrolizumab and vorinostat in ECOG 0-1 patients with immune therapy naïve and immune therapy pretreated locally advanced or metastatic NSCLC who have progressed through one prior line of therapy (**Figure 1**). The study would begin with a phase I dose escalation utilizing the modified continuous reassessment method (O'Quigley, Pepe, & Fisher, 1990). This would be followed by a phase I expansion at the maximum tolerated dose (MTD) in 18 NSCLC patients who have been previously treated with anti-PD-1 or anti-PD-L1 therapy. In parallel, a separate phase II arm will randomize 78 patients to a pembrolizumab alone group and a pembrolizumab plus vorinostat group.

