#### Phase 1b Expansion (Single Arm, Pre-treated Cohort):

**Primary Objective:** To determine whether concurrent administration of vorinostat and Pembrolizumab will be effective in NSCLC patients who have been previously exposed to anti-PD-1 or anti-PD-L1 therapy.

*Hypothesis:* Concurrent administration of vorinostat and Pembrolizumab will be effective in NSCLC patients who have been previously treated with anti-PD-1 or anti-PD-L1 therapy.

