# 4.2.3.1 Efficacy Endpoints

In addition to a baseline scan, confirmatory scans will be obtained 4-6 weeks following initial documentation of objective response. Response and progression will be evaluated in this study using the new international criteria proposed by the revised Response Evaluation Criteria in Solid Tumors (RECIST) guideline (version 1.1)(Eisenhauer et al., 2009). Changes in the largest diameter (unidimensional measurement) of the tumor lesions and the shortest diameter in the case of malignant lymph nodes are used (Schwartz et al., 2009).

Patients who are found to have stable disease (SD), partial response (PR), or complete response (CR) will continue on study until evidence of disease progression, intolerance, or withdrawal from study. Response rate, overall survival, and progression-free survival will be determined. Subjects with progressive disease by RECIST 1.1 but without rapid clinical deterioration may continue to be treated at the discretion of the investigator.

The efficacy analysis will be based on the treated Population which includes all subjects who receive any dose of either investigational product. The following efficacy endpoints will be analyzed.

- Objective response is defined as confirmed CR or confirmed PR based on modified RECIST guidelines version 1.1. The ORR will be estimated by calculating the proportion of subjects who achieve OR; the 80% CI and 95% CI for the OR rate will be estimated using the exact binomial distribution.
- Disease control is defined as CR, PR, or SD based on RECIST guidelines version 1.1 with modifications. The disease control rate (DCR) will be estimated by the proportion of subjects who achieve DC, and its 80% CI and 95% CI will be estimated using the exact binomial distribution.

• Progression-free survival will be measured from the start of treatment with pembrolizumab and vorinostat until the documentation of disease progression or death due to any cause, whichever occurs first. For subjects who are alive and progression-free at the time of data cut-off for analysis, PFS will be censored at the last tumor assessment date. The Kaplan-Meier method (Kaplan and Meier, 1958) will be used to estimate the PFS curve and the PFS rate at time points of interest.

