# 4.2.8 Objective Response Rate

ORR is defined as the number of subjects whose best confirmed objective response (BOR) is a CR or PR, divided by the number of subjects who received at least one dose. BOR is defined as the best response designation, as determined by the RECIST v1.1, recorded between baseline and the date of objectively documented progression per RECIST 1.1 or the date of initiation of palliative local therapy or the date of initiation of subsequent anticancer therapy, whichever occurs first. For subjects without documented progression or palliative local therapy or subsequent anti-cancer therapy, all available response designations will contribute to the BOR determination. The final analysis of ORR will take place at the time of PFS.

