# 5.1.2 Subject Inclusion Criteria

In order to be eligible for participation in this trial, the subject must:

- 1. Be willing and able to provide written informed consent/assent for the trial.
- 2. Be  $\geq$  18 years of age on day of signing informed consent.
- 3. Have measurable disease based on RECIST 1.1.
- 4. Have archival tissue where available. Those patients enrolled on the phase 1 escalation trial where archival tissue is not available will undergo a fresh biopsy where clinically feasible after discussion with the sponsor.

5. In addition, patients enrolled on the phase 1 dose escalation, phase 1 expansion or Phase II trial must be willing and able to provide tissue from a newly obtained core or excisional biopsy of a tumor lesion. Newly-obtained is defined as a specimen obtained up to 3 months prior to initiation of treatment on Day 1, and must be obtained after most recent treatment. Subjects for whom newly-obtained samples cannot be provided (e.g. inaccessible or subject safety concern) may submit an archived specimen only upon agreement from the Sponsor.)

- 6. Randomized phase II: Tumor proportional score of PD-L1 ≥1%.
- 7. Have a performance status of 0 or 1 on the ECOG Performance Scale.
- 8. Demonstrate adequate organ function as defined in **Table 5** all screening labs should be performed within 10 days of treatment initiation.
- 9. Have a histologic or cytologic diagnosis of Stage IV NSCLC.
- 10. Phase I/IB (Pre-treated): Have progression from at least one prior line of therapy. Maintenance therapy following platinum doublet-based chemotherapy is not considered as a separate regimen of therapy. Subjects who received platinum-containing adjuvant, neoadjuvant or definitive chemoradiation therapy given for locally advanced disease, and developed recurrent (local or metastatic) disease within 6 months of completing therapy are eligible for these arms. Subjects with recurrent disease ≥ 6 months after completing a platinum-containing adjuvant, neoadjuvant or definitive chemoradiation therapy given for locally advanced disease, who also subsequently progressed during or after a systemic regimen given to treat the recurrence, must have received another treatment in the first-line metastatic setting.

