#### 8.7.1 Statistical plan for immunogenicity profiles in phase Ib and phase II:

# Phase Ib expansion cohort (PD-1 pretreated: N=18).

Two gene signatures (NF-kB, 12-chemokine genes) will be evaluated to test if they can predict the response to PD-1 blockade + HDACi treatment using the pre-treatment biopsy. For each gene signature, PCA will be used to calculate an index score based on the first principal component. The derived gene signature score will be then used to test if the response group has a higher score than the non-response group using the two-sample t test. A sample size of 18 patients will give an 80% power to detect an effect size of 1.6 with a two-sided 5% type error if the response rate is 30% (i.e., 5 responders and 13 non-

responders) by the two-sample t test. If the response rate is 40% (i.e., 7 responders and 11 non-responders), the power will increase to 87%. We will also test the difference of the score from pre to post-treatment between the responders and non-responders using two-sample t-test. With this sample size (n=18) and 80% power, it will be able to detect an effect size of 1.57 and 1.45 for a response rate of 30% and 40%, respectively with a two-sided 5% type error by the two-sample t-test. In addition, we will also determine association of individual genes with response or resistance, including T cell co-stimulatory and inhibitory genes.

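### Phase Ib entry criteria accept any prior checkpoint drug, although the cohort's objective and analysis are defined by prior anti-PD-1 or anti-PD-L1 therapy

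*Combined protocol and SAP*

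**What the plan says.** **Cohort definition.** Section 2.1 places the expansion "in 18 NSCLC patients who have been previously treated with anti-PD-1 or anti-PD-L1 therapy". The Phase Ib primary objective in section 3.1 concerns "NSCLC patients who have been previously exposed to anti-PD-1 or anti-PD-L1 therapy", and its hypothesis uses the same drug class. The analysis plan in section 8.7.1 is headed "Phase Ib expansion cohort (PD-1 pretreated: N=18"; it names PD-1 without PD-L1, a small further mismatch.

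**Entry criteria.** The note to exclusion 5 in section 5.1.3 states that for Phase Ib "prior use of a PD1 or PDL1, anti-CTLA4 antibody or any other antibody or drug that specifically targets immune checkpoint pathway is required". Exclusion 6 bars "Patients enrolled in the phase Ib expansion who have never previously been treated with a PD1 or PDL1 inhibitor, anti-CTLA 4 antibody" or any other checkpoint-pathway agent. Inclusion item 10 in section 5.1.2 reads "Phase I/IB (Pre-treated): Have progression from at least one prior line of therapy" and names no drug class.

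**Analysis population.** Section 4.2.3.1 makes the efficacy analysis "based on the treated Population which includes all subjects who receive any dose of either investigational product". Section 4.2.8 defines ORR as confirmed responders "divided by the number of subjects who received at least one dose".

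**Looser labels.** The abbreviated title and indication in section 1.0, and the opening sentence of section 2.1, describe these patients only as pretreated with immune therapy.

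**Phase II line of therapy.** Section 1.0 gives second line or later and section 2.1 one prior line, both for the trial as a whole. Section 3.1 and the opening of inclusion item 11 describe Phase II patients as untreated for stage IV disease, with an exception for targeted therapy in driver-mutated tumours. The last sentence of item 11 admits patients who progressed on a systemic regimen for a late recurrence.

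**The concern.** The exclusion 5 note and exclusion 6 use essentially one drug list for three purposes: to exclude in Phase II, to permit in dose escalation and to require in Phase Ib. A broad list joined by 'or' is strict when it excludes and permissive when it requires. In Phase Ib, any one item on the list is enough, so a patient who has never had anti-PD-1 or anti-PD-L1 can enter the cohort set up to study patients who have.

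Phase Ib is single-arm, and its primary question is whether the combination works after anti-PD-1/PD-L1. A patient naïve to that class may respond to pembrolizumab alone. Such a response would be counted as activity in the pretreated population, and the data could not separate the two explanations.

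**Working it through.** **1. Can such a patient enter and be counted?** Take a patient whose only checkpoint drug was an anti-CTLA-4 antibody and who progressed on it.

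- Exclusion 5 note: satisfied.
- Exclusion 6: does not apply, because a listed drug was given.
- Inclusion item 10: satisfied by progression from any prior line.
- Sections 4.2.3.1 and 4.2.8: counted after one dose. Section 8.2.5 likewise includes all enrolled patients.
- Replacement: section 8.2.2 replaces only patients who leave before the end of the DLT period for reasons other than DLT. Section 5.9 has a heading and no text.

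The patient is eligible and is counted, but lies outside the population of the objective.

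**2. Effect of one response.** 1/18 = 5.6 points. Exact binomial intervals at the two levels planned in section 4.2.3.1:

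| Responses | 95% CI | 80% CI |
|---|---|---|
| 0/18 | 0 to 18.5% | 0 to 12.0% |
| 1/18 | 0.1 to 27.3% | 0.6 to 20.0% |

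**3. Expected shift.** With k such patients, response rate q in naïve patients and p in truly pretreated patients, the shift is k(q − p)/18. Section 4.2.1 gives q = 19.4% for pembrolizumab alone in all patients, and 10.7% to 45.2% across PD-L1 strata. The documents give no p, so 5-10% is assumed. They give no k either, so 1 to 3 is illustrative.

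- k = 1: (19.4 − 10)/18 = 0.5 points; (19.4 − 5)/18 = 0.8 points.
- k = 3: 1.6 to 2.4 points.
- Across the PD-L1 strata, k = 1: from (10.7 − 10)/18 = 0.04 to (45.2 − 5)/18 = 2.2 points. At the upper extreme, k = 3 gives 6.7 points.

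The chance of at least one such response is 1 − (1 − q)^k. At q = 19.4% this is 19%, 35% and 48% for k = 1, 2 and 3.

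**4. The plan's own power figures, and the cost of separating these patients.** Section 8.7.1 states 80% power at effect size 1.6 for 5 responders against 13 non-responders, and 87% for 7 against 11 (two-sample t test, two-sided 5%). With noncentrality d√(n₁n₂/(n₁+n₂)) and n₁+n₂−2 degrees of freedom:

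- 5 vs 13: noncentrality 1.6 × √(65/18) = 3.04, power 81.4%.
- 7 vs 11: noncentrality 1.6 × √(77/18) = 3.31, power 87.4%.

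Both stated figures are reproduced. If k patients are analysed separately, with a 30% response rate and responder counts rounded down, and with the zero-response upper limit 1 − 0.025^(1/n):

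| k | n | 95% upper limit at 0 responses | Split | Power at d = 1.6 |
|---|---|---|---|---|
| 0 | 18 | 18.5% | 5 vs 13 | 81.4% |
| 1 | 17 | 19.5% | 5 vs 12 | 80.2% |
| 2 | 16 | 20.6% | 4 vs 12 | 73.2% |
| 3 | 15 | 21.8% | 4 vs 11 | 71.7% |

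**The case against.** **The broad criterion may be what was meant.** The title, the indication and the opening of section 2.1 use the wider immune-therapy label. Section 5.1.3 also draws the naïve/pretreated contrast with the wide drug list in both directions. This stands: the documents do not show which side is the slip, only that the two sides disagree. It does not remove the problem, because the objective and cohort definition remain narrower than the entry rule.

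**Exclusion 16 could catch these patients.** It lets the treating investigator exclude a patient whose prior therapy might confound the results. It is a matter of opinion, and it cannot be relied on to bar a patient whom the exclusion 5 note expressly accepts.

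**The effect is small.** This also stands. An expected shift of 0.5 to 0.8 points per patient is slight beside a 95% interval about 27 points wide at 1/18.

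**Stronger readings that a reader might infer, and that the documents do not support:**

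- *Patients with no checkpoint exposure can enter Phase Ib.* Exclusion 6 bars them.
- *The gene-signature test is biased.* The first secondary hypothesis (section 3.2) and section 8.7.1 test whether the signature predicts response. They do not attribute response to vorinostat, so a response driven by pembrolizumab is still a valid response for that test.
- *A Phase Ib go/no-go decision could be reversed.* No threshold is stated.
- *Phase II mixes lines of therapy in a way that undermines its 25% and 45% benchmarks.* Section 8.2.6 states no line of therapy for them. The last sentence of item 11 can be read as a second exception to its opening, and items 10 and 11 treat that patient compatibly.

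**Conclusion.** The Phase Ib contradiction is real. The written entry rule admits patients naïve to anti-PD-1/PD-L1 into a single-arm cohort whose objective concerns patients exposed to those drugs, and no analysis rule removes them. The likely bias is towards efficacy: 5.6 points for each such response observed, but about 0.5 to 0.8 points expected per such patient. The expected figure rests on the assumed 5-10% response in truly pretreated patients and the 19.4% in section 4.2.1. The number of such patients is unknown and probably small. No stated design figure is wrong because of this; the weakness lies in the estimate and its interpretation.

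The Phase II line-of-therapy statements are a minor matter of wording.

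**What to change.** Reconcile the exclusion 5 note and exclusion 6 with sections 2.1, 3.1 and 8.7.1. Either option would do, and the choice is the sponsor's:

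1. Align the two criteria with the anti-PD-1/PD-L1 definition, with other checkpoint drugs counting only in addition. The sample size stays at 18 and the power is unchanged; a few patients become ineligible.
2. If the wider criterion is intended, restate the objective. Prespecify the primary response rate in anti-PD-1/PD-L1-exposed patients, report the others separately, and write this into sections 4.2.3.1 and 4.2.8. The cost for one to three separated patients is a zero-response 95% upper limit of 19.5-21.8% instead of 18.5%. If the signature test is restricted in the same way, its power at 30% response falls from about 81% to 72-80%.

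Neither option removes responses to pembrolizumab alone in patients who were exposed to anti-PD-1/PD-L1 but did not progress on it, because item 10 accepts progression from any line and the objective asks only for exposure. The report should say so.

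Minor wording: limit the line-of-therapy statements in sections 1.0 and 2.1 to the trial parts they describe, and state whether the last sentence of item 11 is an exception to its opening. All of this is a text amendment.

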#### **5.2 Trial Treatments**

The phase I dose escalation will include a fixed dose of Pembrolizumab 200mg IV every 3 weeks and escalating doses of vorinostat (three dose levels) to determine the MTD to be used in the expansion group and the randomized phase II portion of the trial. Once a MTD is determined, the phase Ib expansion and randomized phase two portions of the trial can begin accrual. Cycle 1, day 1 will start with Pembrolizumab concurrent with continuous daily oral therapy with vorinostat.

Table 6. Vorinostat dose levels in phase I dose escalation phase.

Dose Level	Vorinostat Dose, Route, Frequency	Pembrolizumab Dose, Route, Frequency	Use
-1	100mg PO Daily	200mg IV Q3 weeks	Experimental
1	200mg PO Daily	200mg IV Q3 weeks	Experimental
2	400mg PO Daily	200mg IV Q3 weeks	Experimental

Trial treatment should begin within 3 days of randomization or as close as possible to the date on which treatment is allocated/assigned.

